4.6.1 Primary efficacy endpoints

There is no primary efficacy analysis. The primary analysis for study CSL830_3002 is safety-based and can be found in [Section 4.7.1](#).

4.6.2 Method of analysis for primary efficacy endpoint

Not applicable.

4.6.3 Secondary efficacy endpoints

Secondary efficacy endpoints are:

- a. The percentage of subjects who are responders. The “response” is defined as a $\geq 50\%$ relative reduction in the time-normalized number of HAE attacks during treatment with CSL830, compared with the time-normalized number of attacks that is used to qualify the subject for participation in this study (see Section 4.1.2 of the protocol [inclusion criterion 5]).
- b. The percentage of subjects who experience a time-normalized number of HAE attacks of < 1 HAE attack per 4-week period.

The time-normalized number of HAE attacks during treatment with CSL830 is calculated per subject as:

- The number of HAE attacks /length of stay of subject (days);

where the length of stay for subjects who are not participating in the Extension Period is calculated as:

- Date of End of Study Visit at Week 53, date of the 4th day post the last IMP administration or study discontinuation date (whichever occurs first) – date of Day 1 Week 3 + 1.

for HAE attacks with start date before (including) the Week 53 visit, the last administration of CSL830 + 4 days or study discontinuation date (whichever occurs first).

For subjects who are continuing into the Extension Period and have no rest period, the length of stay is calculated as:

- Date of End of Study Visit at Week 88, date of the 4th day post the last IMP administration or study discontinuation date (whichever occurs first) – date of Day 1 Week 3 + 1.

for HAE attacks with start date before (including) the Week 88 visit, the last administration of CSL830 + 4 days or study discontinuation date (whichever occurs first).

For subjects who are continuing into the Extension Period and have a rest period, the length of stay is calculated as:

- {Date of End of Study Visit at Week 53, date of the 4th day post the last IMP administration in Treatment Period 2 (whichever occurs first) – date of Day 1 Week 3 + 1} + {Date of End of Study Visit at Week 88, date of the 4th day post the last IMP administration in the Extension Period or study discontinuation date (whichever occurs first) – date of first visit of the Extension Period + 1}.

for HAE attacks with start date outside the rest period and before (including) the Week 88 Visit or the last administration of CSL830 + 4 days or study discontinuation date (whichever occurs first).

HAE attacks with start dates

- between one day after the End of Study Visit or 4th day post last IMP administration [whichever occurs first] and the Follow-up Visit of Treatment Period 2 (applicable for subjects not participating in the Extension Period)
- between one day after the End of Study Visit or 4th day post last IMP administration [whichever occurs first] and the Extension Follow-up Visit (applicable for subjects participating in the Extension Period)
- between one day after the Week 53 Visit or 4th day post last IMP administration [whichever is first] of Treatment Period 2 and the first visit of the Extension Period (applicable for subjects who are taking part in the Extension Period and who have a rest period)

will not be included in the analyses (ie the numerator “number of HAE attacks”).

4.6.3.1 The percentage of subjects who are responders

The percentage reduction in the time-normalized number of HAE attacks per subject is calculated as:

- $100\% * [1 - (\text{the time-normalized number of HAE attacks when treated with CSL830}) / (\text{the time-normalized number of HAE attacks used to qualify for participation in the current study})]$

The HAE attacks used to qualify for participation in the current study are derived from the subject medical records:

- “CSL830-Naïve” Subjects using intravenous C1-INH as routine (long-term) prophylaxis against HAE attacks must have experienced 4 HAE attacks over *any* consecutive 2-month period before the initiation of intravenous C1-INH prophylaxis and before the CSL830_3002 Screening Visit, as documented in the subject medical records.

- All other “CSL830-Naïve” Subjects (e.g., treated using oral HAE prophylaxis against HAE attacks or on-demand treatment) must have experienced 4 HAE attacks over a consecutive 2-month period within the 3 months before the CSL830_3002 Screening Visit, as documented in the subject medical records.
- For “CSL830-Continuation” Subjects and “CSL830-Interrupted” Subjects: Subjects must have experienced 4 HAE attacks over a consecutive 2-month period within the 3 months before the CSL830_3001 Screening Visit, as documented in the subject medical records (i.e., the HAE attack frequency required for eligibility to participate in study CSL830_3001).

A subject is classified as a responder if the percentage reduction is $\geq 50\%$. A subject whose time-normalized number of attacks cannot be calculated in the treatment periods will be excluded from the calculation of the percentage of responder analysis.

The number and percentage of responders and non-responders and the difference in the percentage of responder between the 60IU/kg CSL830 and 40IU/kg CSL830 treatments will be summarized. 95% Wilson Confidence Intervals will be calculated for all percentages.

The analyses will be repeated including only subjects who have no dose increase.

Subgroup analyses will be performed for age (≤ 17 years / >17 years) and subjects' completion status (completed study / discontinued early). The number and percentage of responders and non-responders will also be calculated and presented descriptively for each of the following time windows:

- 1) For all subjects: every 6 months excluding the first 2 weeks in Period 1 (for subject who are participating in the Extension Period and who have a rest period: the rest period will also be excluded),
- 2) For subjects who are not participating in the Extension Period: first 6 months and first 12 months excluding the first 2 weeks in Period 1,
- 3) For subjects who are participating in the Extension Period: first 6 months, first 12 months, first 18 months and first 22 months excluding the first 2 weeks in Period 1 (for subject who have a rest period: the rest period will also be excluded).

Subjects who undergo a dose increase will be flagged in the listing.

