1.2.3 Previous Clinical Experience

Currently, clinical data are available from two studies that were conducted with CSL830: study CSL830_1001 and study CSL830_2001.

Study CSL830_1001 was conducted in healthy subjects in order to compare the safety and PK of intravenously administered CSL830 and Berinert (the currently marketed C1-INH concentrate). CSL830 had acceptable safety and local tolerability profiles. There were no adverse events (AEs) causally related to CSL830 or Berinert, and there were no clinically significant abnormalities in laboratory parameters, viral safety assessments, vital signs, physical examinations, or electrocardiogram results. No anti-C1-INH antibodies were detected in any subject. There were no thromboembolic events (TEEs), and no surrogate markers suggestive of pulmonary embolism (PE) or deep vein thrombosis (DVT) were identified. CSL830 and Berinert also had comparable PK profiles following single-dose, IV administration.

Study CSL830_2001 was conducted in subjects with HAE (type I or II) in order to characterize the PK, pharmacodynamics (PD), and safety of SC administration. Functional levels of C1-INH activity and levels of C1-INH antigen and C4 antigen were achieved with each CSL830 dosing regimen that was tested. Subcutaneous administration of CSL830 of up to 6,000 IU was tolerated with local site events. Safety events were not related to either absolute CSL830 dose or dose per body weight. There was no evidence of a dose-response relationship between the administered dose of CSL830 and the intensity of treatment-emergent adverse events (TEAEs). Inhibitory auto- antibodies to C1-INH did not develop in any of the subjects in the study. Further, there were no TEEs.

The efficacy and safety of SC CSL830 are currently being assessed in a double-blind, randomized, placebo-controlled, crossover phase 3 study (study identifier CSL830_3001) that is enrolling at least 80 subjects with HAE. During participation in CSL830_3001 subjects are randomly assigned to either a 40 IU/kg CSL830 or 60 IU/kg CSL830 treatment sequence. Each sequence consists of 2 consecutive treatment periods. Each subject receives the assigned dose of CSL830 in 1 treatment period and placebo in the other treatment period. Subjects who participate in study CSL830_3001 will be eligible to participate in this long-term safety study if they meet all eligibility criteria (see [Section 4.1](#)).

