4.1.2 Inclusion Criteria

Subjects meeting all of the following inclusion criteria may be enrolled (randomized) into the study:

1. Capable of providing written informed consent/assent (as appropriate) and willing and able to adhere to all protocol requirements, and/or the subject’s parent(s) or legally acceptable representative(s) capable of providing written informed consent.
2. Male or female.
3. Aged 6 years or older at the time of providing written informed consent/assent (as appropriate).
4. A diagnosis of HAE (type I or II), as determined by the following: a clinical history consistent with HAE *and* CCI [REDACTED]
[REDACTED]
 - For “CSL830-Naïve” Subjects: Historically documented CCI [REDACTED]
[REDACTED] that are compatible with participation will be accepted; however, if historical documentation is unavailable, then the tests may be conducted at Screening. Biochemical confirmation of HAE (type I or II) diagnosis must be established for a subject before starting the Treatment Period 1.
 - For “CSL830-Interrupted” Subjects AND “CSL830-Continuation” Subjects: The documentation that was used to confirm eligibility in CSL830_3001 will be used to verify the required value for inclusion in the current study (CSL830_3002).
5. Have experienced HAE attacks (requiring acute treatment, medical attention or causing significant functional impairment) as described below:

- For “CSL830-Naïve” Subjects:
 - “CSL830-Naïve” Subjects using intravenous C1-INH as routine (long-term) prophylaxis against HAE attacks must have experienced 4 HAE attacks over *any* consecutive 2-month period before the initiation of intravenous C1-INH prophylaxis and before the CSL830_3002 Screening Visit, as documented in the subject medical records.
 - All other “CSL830-Naïve” Subjects (eg, treated using oral HAE prophylaxis against HAE attacks or on-demand treatment) must have experienced 4 HAE attacks over a consecutive 2-month period within the 3 months before the CSL830_3002 Screening Visit, as documented in the subject medical records.
 - For “CSL830-Continuation” Subjects AND “CSL830-Interrupted” Subjects:

Subjects must have experienced 4 HAE attacks over a consecutive 2-month period within the 3 months before the CSL830_3001 Screening Visit, as documented in the subject medical records (ie, the HAE attack frequency required for eligibility to participate in study CSL830_3001).

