4.14 Changes in Conduct or Planned Analyses from the Protocol

The statistical analysis for the original protocol and the Extension Period amendment are described in the one SAP to be on hand and not in two different statistical analysis plans.

The data from Treatment Period 1, Treatment Period 2, and Extension Period will be analyzed and presented jointly. Data collected from subjects who are enrolled in the Extension Period will be analyzed together with the data of subjects who are not participating in the Extension Period.

Because of the assumption that a minority (e.g., less than 20%) of subjects will undergo a CSL830 dose increase during the study, the first and second approaches as specified in 11.3.3 of the protocol will not be performed for the secondary safety endpoints. Rather, the approach to safety analysis based upon the actual treatment (40 IU/kg CSL830, 60 IU/kg CSL830 and ≥ 40 IU/kg CSL830) at the time of the event will be performed for the safety analyses.

The analyses by subjects who are randomized to 40 IU/kg CSL830 and who have 1 dose increase; by subjects who are randomized to 40 IU/kg CSL830 and who have 2 dose increases; by subjects who are randomized to 60 IU/kg CSL830 and who have 1 dose increase will not be done.

A treatment group ≥ 40 IU/kg CSL830 has been added in the analyses by treatment and overall group has been deleted.

If an event or evaluation occurred while a subject was receiving 80 IU/kg, these data will be listed and summarized in the ≥ 40 IU/kg CSL830 treatment group.

Adverse events that occur during the Screening will not be summarized for subjects in the Safety Population and will only be listed.

Safety and some efficacy analyses will not be performed for age group. No subgroups of subjects who previously used intravenously administered C1-INH for routine (long-term) prophylaxis will be assessed.

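### The responder percentage is measured against the attack window that admitted the subject, so it includes regression to the mean, and no readable analysis uses another baseline

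*SAP*

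**What the plan says.** Protocol 2.2.2 and SAP 4.6.3 define response as a fall of at least 50% in the time-normalized attack number. The denominator in SAP 4.6.3.1 is "the time-normalized number of HAE attacks used to qualify for participation in the current study".

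The same section gives the source of that number: "The HAE attacks used to qualify for participation in the current study are derived from the subject medical records". Three windows follow, matching inclusion criterion 5 in Protocol 4.1.2:

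- **Continuation and Interrupted subjects:** "Subjects must have experienced 4 HAE attacks over a consecutive 2-month period within the 3 months before the CSL830_3001 Screening Visit".
- **Naïve subjects not on intravenous C1-INH prophylaxis:** "must have experienced 4 HAE attacks over a consecutive 2-month period within the 3 months before the CSL830_3002 Screening Visit".
- **Naïve subjects on intravenous C1-INH prophylaxis:** 4 attacks at whatever point in the past, the window being a "consecutive 2-month period before the initiation of intravenous C1-INH prophylaxis and before the CSL830_3002 Screening Visit, as documented in the subject medical records". No look-back limit is set.

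On the preceding study, Protocol 1.2.3 says: "Each subject receives the assigned dose of CSL830 in 1 treatment period and placebo in the other treatment period". Rollover subjects completed that study (Protocol 4.1.1), and those withdrawn from it are excluded (Protocol 4.1.3, criterion 1).

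SAP 4.6.3.1 reports responder percentages with Wilson intervals and the 60 minus 40 IU/kg difference. The readable variations concern attack merging, analysis population, dose-increase status, time window, age and completion status. None changes the baseline. SAP 4.14 adds: "No subgroups of subjects who previously used intravenously administered C1-INH for routine (long-term) prophylaxis will be assessed".

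**The concern.** The window that admits a subject is also the yardstick for response. Attack counts fluctuate, and a window that had to reach 4 attacks is on average higher than the subject's long-run rate. Part of the later fall would therefore occur without any drug. There is no untreated arm to show how much.

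The responder percentage is one of two secondary endpoints for the efficacy objective, and its Wilson interval covers sampling error only. The selection also differs by class of subject: a 3-month look-back for most, an unlimited history for Naïve subjects on intravenous C1-INH prophylaxis. A pooled figure mixes the two. The pre-study versus on-treatment comparison of attack numbers in SAP 4.6.3.2 may be affected in the same way, depending on which pre-study count is used.

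**Working it through.** **1. The plan's own figure.** Neither document gives a sample size, power or expected percentage for this endpoint. The one design figure (Protocol 11.1, SAP 3.8) is 100 subjects and an event probability of 3%: 1 − 0.97^100 = 95.2%. It reproduces but does not bear on response.

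**2. Inputs.**

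- From the documents: entry at 4 attacks in 2 months; response at a 50% reduction; efficacy observation from Week 3 Day 1 (SAP 4.6). Day 15 to Day 365, the lower end of the Week 53 window, is 365 − 15 + 1 = 351 days.
- Assumed: 2 months = 61 days; Poisson counts; the subject's true rate; the spread of rates between subjects; the actual count in the qualifying window as numerator of the baseline rate; a placebo period of 8 or 14 weeks (its length is not given).

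**3. One fixed window, no drug effect, exact.** Let X be Poisson with mean m attacks per 2 months, and require X ≥ 4. The on-study count Y is Poisson with mean m × 351/61. The subject responds if Y ≤ 0.5 × X × 351/61 = 2.877 X. So

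P(response) = Σ over x ≥ 4 of P(X = x) · P(Y ≤ 2.877x) ÷ P(X ≥ 4).

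| True rate per 2 months | Chance responders |
|---|---|
| 8 | 1.9% |
| 6 | 3.9% |
| 4 | 12.4% |
| 3 | 26.8% |
| 2 | 64.5% |

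The mechanism is visible at m = 4. The mean qualifying count is m · P(X ≥ 3)/P(X ≥ 4) = 4 × 0.762/0.567 = 5.38, so the baseline overstates the true rate by about a third (5.38/4 = 1.34).

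**4. Highest 2 months of 3, no drug effect, simulated.**

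- Mean 1.5 to 4 attacks per month, gamma shape 1.5 or 4 between subjects: about 6% to 27% chance responders without month-to-month variation, and up to 41% with it.
- A second run with mean 1 to 4 per month and shape 0.5 to 4: 7.7% to 45.5% (5.0% to 66.9% if the case where all subjects share one rate is included). The qualifiers' true rate was 0.55 to 0.85 of their qualifying rate.
- Dividing the whole 3-month count by 3, as SAP 4.4 does for the baseline table, lowers the first set to 2% to 24%.

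**5. Same subjects, independent placebo-period baseline, no drug effect.** In the second run, chance responders fall to 2.8% to 13.5% (8 weeks) or 1.4% to 8.1% (14 weeks). About 0.7% to 11% (8 weeks) or 0.1% to 2.6% (14 weeks) have no placebo attacks, so their percentage reduction is undefined.

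**6. With a drug effect.** Under the assumptions of the first run without month-to-month variation, and leaving out subjects with no placebo attacks, the qualifying-window percentage exceeds the placebo-baseline percentage by:

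| True reduction | Gap |
|---|---|
| 50% | 20 to 35 points |
| 80% | about 3 to 9 points |
| 90% | about 0.5 to 2 points |

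Not all of this gap is inflation. At a true 80% reduction, noise in the placebo denominator alone turns 3% to 9% of subjects into non-responders.

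**The case against.** The strongest case on the other side has five parts.

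- **Role.** There is no primary efficacy analysis. Efficacy is only to be characterized, and CSL830_3001 is the pivotal placebo-controlled study (Protocol 1.4). The responder definition was pre-specified and carries no test. This stands: the issue is how a percentage is read, not type I error.
- **Comparison of doses.** A reader might infer that the bias favours 60 over 40 IU/kg. The documents do not support that. Randomization is stratified by roll-over class (Protocol 6.1.2, SAP 3.6), and the same kind of baseline serves both arms. The endpoint of fewer than 1 attack per 4 weeks uses no baseline and is unaffected.
- **Size.** A reader might infer that most responders are artefact, since assumed histories of 12 or 24 months give 21% to 66% or 32% to 80% chance responders. Those look-back lengths are not in the documents, and they concern only Naïve subjects on intravenous C1-INH prophylaxis, whose number is not stated. Nor do the documents say that sites record the highest window, or which count is divided by which length. This stands, and it limits what can be said about magnitude.
- **Use of the placebo rate.** A reader might infer that the SAP nowhere uses it. The exploratory sections are blacked out, so only the readable text can be judged.
- **Remedy.** The placebo rate is not from an unselected group: rollover subjects met the 4-attack criterion and completed CSL830_3001. It was merely not used for selection. It is noisier, can be zero, and comes from a study whose attack-merging rule and possible carry-over are not described here. This justifies a supportive role, not replacement of the endpoint.

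SAP 4.14 does record openly that the prior-prophylaxis subgroup was dropped. Restoring it would display that group without correcting its baseline.

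**Conclusion.** The point holds as a matter of interpretation. Each arm's responder percentage includes regression to the mean, and the readable text offers no version with another baseline, although rollover subjects have one.

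The size cannot be fixed from the documents. With no drug effect it is roughly 2% to 12% of subjects for one fixed window at true rates of 8 down to 4 per 2 months, and roughly 6% to 41% if the highest 2 months of 3 is recorded. It is larger if true rates lie below the entry threshold. If the drug effect is large, little changes: a gap of about 3 to 9 points at a true 80% reduction and about 2 or less at 90%, part of it placebo noise. These figures rest on assumed rates, Poisson counts, use of the actual window count and assumed placebo-period lengths.

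The documents do not support a claim that the dose comparison is biased or that the efficacy objective as a whole fails. This is a cheap improvement to the SAP.

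**What to change.** Keep the protocol-defined endpoint and amend SAP 4.6.3.1 as follows.

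1. State which count and which length form the qualifying rate, and that the resulting percentage includes regression to the mean.
2. For Continuation and Interrupted subjects, add a supportive responder analysis with each subject's own CSL830_3001 placebo-period attack rate as denominator. Apply the attack-merging rule of SAP 4.6 to both studies. Fix a rule for zero placebo attacks, for example counting them as non-responders, with a second version that excludes them. The choice can matter by up to the share of such subjects (up to about 11% in the 8-week runs above).
3. For Naïve subjects not on intravenous C1-INH prophylaxis, add a version with the whole 3-month pre-screening rate of SAP 4.4. This reduces the bias but does not remove it, because the 3 months contain the qualifying window.
4. Show the result by roll-over class, and restore the prior intravenous C1-INH subgroup of Protocol 11.3.2.2 as a display.

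The cost is SAP wording and a merge with the sponsor's CSL830_3001 attack data. Conduct, sample size and the primary safety analysis are untouched. The supportive percentage will probably be somewhat lower than the main one, and its denominator is noisier.

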3.5 Planned Number of Subjects

The study plans to enroll subjects who complete participation in CSL830_3001. Additional subjects who have not participated in study CSL830_3001 will be enrolled so that the total number of subjects randomized is approximately 110.

Assuming that up to 10% of subjects withdraw before the completion of the study, 100 subjects are planned to complete the study.

Subjects from the United States who have completed Treatment Period 1 and Treatment Period 2 according to the study protocol are eligible to enroll in the Extension Period. Approximately 50 of these subjects are anticipated to enroll in the Extension Period.

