11.3.2.2 Secondary Efficacy Analyses

The ITT and PP Populations will be used as analysis populations for efficacy analyses.

Treatment Period 1 and Treatment Period 2

All subjects in the ITT and all subjects in the PP Population will be used as analysis populations for efficacy analyses. The number and percentage of subjects who are responders at the last visit in Treatment Period 1 and at the last visit in Treatment period 2, when “response” is defined as a $\geq 50\%$ relative reduction in the time-normalized number of HAE attacks during treatment with CSL830, compared with the time-normalized number of attacks used to qualify for participation in the current study will be assessed. The number and percentage of subjects will be summarized (by subjects who are randomized to 40 IU/kg CSL830; and by subjects who are randomized to 60 IU/kg CSL830). Subjects who undergo a dose increase will be flagged in the listing.

The number and percentage of subjects who experience a time-normalized HAE attack frequency of < 1 HAE attack per 4-week period will be summarized at the last visit in Treatment Period 1 and at the last visit in Treatment Period 2 (by subjects who are randomized to 40 IU/kg CSL830 and by subjects who are randomized to 60 IU/kg CSL830). Subjects who undergo a dose increase will be flagged in the listing.

A within-subject analysis will give the number and percentage of subjects who are responders or non-responders before a dose increase, after a first dose increase, and after a second dose increase (only applicable for subjects who are randomizes to the 40 IU/kg CSL830 treatment group) summarized by subjects who are randomized to the 40 IU/kg CSL830 and by subjects who are randomized to the 60 IU/kg CSL830 treatment group. Furthermore, a within-subject analysis will give the number and percentage of subjects who experience or who do not experience a time-normalized HAE attack frequency of < 1 HAE attack per 4-week period before a dose increase, after a first dose increase, and after a second dose increase (only applicable for subjects who are randomizes to the 40IU/kg treatment group) summarized by

subjects who are randomized to the 40 IU/kg and by subjects who are randomized to the 60 IU/kg treatment group.

The secondary efficacy analyses will be done both for Treatment Period 1 (only) and for Treatment Periods 1 and 2 (together).

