3.4.1 Intent to Treat Population

The Intent to Treat (ITT) Population will comprise all subjects who provide informed consent/assent (as appropriate) and are randomized, regardless of whether or not they receive CSL830. Subjects in the ITT Population will be analyzed as randomized.

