3.8 Sample Size

100 subjects are planned to complete the study. The sample size is based on guidelines issued by the International Conference on Harmonisation, ICH 1994 [1] and not on statistical calculations. The sample size of 100 subjects allows observation of ≥ 1 adverse event with a probability of 3% at 95% confidence.

4 Statistical Methodology

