4.6 Efficacy Analysis

The secondary efficacy analyses will be carried out for the ITT and PP Populations. The ITT Population is used as the primary analysis and the Per Protocol Population will be used as secondary analysis.

The evaluation period for efficacy assessments will be from the start (Day 1) of Week 3 of a treatment in Treatment Period 1 until the End of Study Visit (Week 53 Visit) or the last administration of CSL830 + 4 days (whichever occurs first) for subjects who are not participating in the Extension Period. For subjects who are taking part in the Extension Period, the evaluation period will be from the start (Day 1) of Week 3 of the treatment in Treatment Period 1 until the End of Study Visit of the Extension Period (Week 88) or the last administration of CSL830 + 4 days (whichever occurs first). For subjects who are participating in the Extension Period and who have a rest period between Treatment Period 2 and the Extension Period, the evaluation period will exclude the rest period between the Week 53 Visit or the last administration of CSL830 + 4 days (whichever occurs first) of Treatment Period 2 and the first visit of the Extension Period.

CCI

Each day, subjects are to enter HAE symptoms (yes/no) into their eDiary and, if yes, the severity(s) and location(s) of the HAE symptom(s). Investigator-reported HAE attacks are based upon review of patient diaries and review of relevant interim medical history, including hospital/medical records and any information provided by the subject. Using medical judgment, the investigator is to determine the occurrence of an HAE attack and report its start and stop dates (generally from onset of the first symptom preceded by symptom-free day to the last symptom preceding symptom-free day), its severity (based upon maximal intensity of any symptom as judged by the investigator), and its location(s) (all involved locations as judged by the investigator are to be reported). Each HAE attack is to be preceded and followed by an attack-free day. For every visit, the Investigator is to report all HAE attacks that have occurred in the interim since the last visit the subject attended.

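### The primary ITT responder analysis drops randomized subjects with no evaluable time and sets no minimum evaluable time; the likely effect is small but the rule contradicts the stated population

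*SAP*

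**What the plan says.** SAP 3.4.1 defines the ITT Population as consenting subjects who "are randomized, regardless of whether or not they receive CSL830". SAP 4.6 adds, for efficacy, "The ITT Population is used as the primary analysis", with Per-Protocol as secondary. Protocol 11.3.2.2 agrees: "All subjects in the ITT and all subjects in the PP Population will be used as analysis populations for efficacy analyses".

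SAP 4.6.3 computes each subject's rate as attacks divided by days. The days run from Day 1 of Week 3 to the earliest of the final visit, the fourth day after the last injection, and discontinuation. SAP 4.6.3.1 compares this rate with the qualifying rate and calls a reduction of at least 50% a response. A subject without a calculable rate "will be excluded from the calculation of the percentage of responder analysis".

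No section sets a minimum number of evaluable days. SAP 4.12 plans no imputation, and its reasoning concerns only the primary safety endpoints. SAP 4.14, which lists changes from the protocol, does not mention this exclusion. SAP 4.6.3.2 reuses the same rate, multiplied by 28, for the endpoint of fewer than 1 attack per 4 weeks. It does not say what happens when the rate is missing.

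**The concern.** Two separate gaps meet here.

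- **Population.** A percentage that leaves out some randomized subjects is not an analysis of the ITT set as defined. The omission depends on what happens after randomization, and SAP 4.6.3.1 also summarizes the difference between 60 and 40 IU/kg. Unequal early loss between the arms would therefore carry into that difference.
- **Minimum time.** With no floor on follow-up, one attack-free evaluable day gives a 100% reduction and a responder. A short stay with one attack gives a very high rate and a non-responder, whatever the subject's true response.

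At stake is how far the reported responder percentage can be read as the proportion of all randomized subjects who responded.

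**Working it through.** **The plan's own figures.** The only numerical design statement is that 100 completers "allows observation of ≥ 1 adverse event with a probability of 3% at 95% confidence" (SAP 3.8). Read as an event with 3% probability being seen at least once: 1 − 0.97^100 = 95.2%, which reproduces it. Protocol 3.5 gives about 110 randomized and up to 10% withdrawing: 110 × 0.9 = 99, consistent with 100 completers. Neither document states an expected responder rate or number of non-evaluable subjects, so those are assumed below.

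**Who is removed.** Evaluable time starts on Day 15. If the last injection is on day d and sets the end of the interval, length = (d + 4) − 15 + 1 = d − 10. A last injection on Day 10 gives 0 days, and Day 11 gives 1 day. Subjects never treated, last injected on or before Day 10, or discontinued before Day 15 have no positive evaluable time.

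**Direction.** With x responders among n randomized and m not evaluable, the plan reports x/(n − m). Counting the m as non-responders gives x/n. The excess is x·m / [n(n − m)], which is never negative.

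**Size of the exclusion (counts assumed).**

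| Not evaluable | As planned | All randomized | Excess |
|---|---|---|---|
| 1 of 110 | 88/109 = 80.7% | 88/110 = 80.0% | 0.7 points |
| 3 of 110 | 86/107 = 80.4% | 86/110 = 78.2% | 2.2 points |
| 5 of 110 (upper-end case) | 88/105 = 83.8% | 88/110 = 80.0% | 3.8 points |

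**How many to expect.** If 11 withdrawals (10% of 110) were spread evenly over 367 days (an assumption), 11 × 14/367 = 0.4 would leave before Day 15. With fewer than 28 evaluable days (gone by Day 41), the number would be 11 × 41/367 = 1.2.

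**Short stays.** The minimum qualifying rate is 4 attacks in 2 months. Taking 2 months as 365.25/6 = 60.9 days, this is 0.0657 per day, so the response threshold is 0.0329 per day. One attack meets it only from 1/0.0329 = 30.4 days (28 days if 2 months is taken as 56 days, 30 if 60). Assuming Poisson attacks at this lowest qualifying rate:

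- No drug effect, scored a responder: exp(−0.0657 × t) = 94% at 1 day, 63% at 7, 40% at 14 and 16% at 28. At 351 days (Day 15 to Day 365) up to 11 attacks are allowed, and the probability is 0.4%.
- True 80% reduction, scored a non-responder at 28 days: 1 − exp(−0.2 × 0.0657 × 28) = 31%.

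The no-effect figures fall at higher qualifying rates. At twice the rate, the 7-day figure is about 40% and the 14-day figure about 16%.

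For the 4-week endpoint, one attack in t days gives 28/t, which is below 1 only when t exceeds 28. The same two-way misclassification applies.

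**The case against.** The best defence has four parts.

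- **Few subjects are affected.** Randomization and a supervised first injection take place at the same Day 1 visit (Protocol 8.4.3.1), and subjects withdrawn from CSL830_3001 are not eligible (Protocol 4.1.3). This stands, and it is why the expected effect is small.
- **The endpoint is defined during treatment, so an untreated subject has no value.** This is reasonable, and the exclusion is openly pre-specified. But it argues for naming a treated and evaluable population, not for calling the result ITT.
- **The SAP already shows early leavers.** It plans responders by completion status and by time window (4.6.3.1), population counts and discontinuation reasons (4.3), and a pre-lock listing of untreated subjects (4.11). These help a reader trace the excluded subjects. They do not restore them to the percentage or set a minimum time.
- **A 28-day cut-off overrides observed data and is somewhat arbitrary.** This stands, and it limits that rule to a sensitivity analysis.

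A reader might also infer that early leavers are always either removed or scored as responders, so that drop-out can only inflate the result. The documents do not support that. Anyone with at least one evaluable day keeps the observed rate. At the minimum qualifying rate, one attack in under about 30 days is scored as non-response, and subjects who leave late have ample follow-up.

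**Conclusion.** The point holds in this limited form. The responder rule contradicts the ITT definition, and relative to non-responder counting the exclusion can only raise the percentage or leave it unchanged. The missing minimum time is a separate weakness whose net direction is not known.

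The likely size of the exclusion is about 0.7 points with 1 of 110 not evaluable and about 2 points with 3, assuming roughly 80% response. The case of 5 of 110 would put almost half of the 11 expected withdrawals into the first two weeks. The 94% to 16% figures assume no drug effect, the lowest qualifying rate and Poisson attacks; they show the mechanism and do not forecast the trial.

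A reader might take the 10% withdrawal allowance to imply a shift of 8 to 10 points. At 80% response among 99 completers, 79/110 = 71.8% would become 79/99 = 79.8% with all 11 removed, or 90/110 = 81.8% with all 11 scored as responders. That needs every withdrawal to come before evaluable time starts, or every leaver to be scored a responder. Protocol 3.5 allows 10% over the whole study, so this is only an outer bound.

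The endpoint is secondary and descriptive, with no test specified, so no power or alpha figure changes.

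**What to change.** In SAP 4.6.3.1, for the ITT analysis:

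1. Keep all randomized subjects in the denominator and count those without a calculable rate as non-responders.
2. Report the number of such subjects in each arm.
3. State the same rule in SAP 4.6.3.2, counting such subjects as not having achieved fewer than 1 attack per 4 weeks.
4. As a sensitivity analysis only, repeat both endpoints with subjects having fewer than about 28 evaluable days counted as non-responders.
5. Record the handling in SAP 4.14.

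The cost is SAP wording and minor programming; no new data are needed. The downside is a slightly lower responder percentage, and the sensitivity analysis overrides some genuinely observed short-stay data, which its footnote should say.
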